## 5 Study Variables

### 5.1 Baseline Characteristics Variables

Following baseline characteristics will be collected and described:

- Age
- Sex (male, female)
- Mechanical ventilation (yes, no)
- Maximum heart rate (0-24 hours before intervention)
- Minimum systolic blood pressure (0-24 hours before intervention)
- Maximum respiratory frequency (0-24 hours before intervention)
- Maximum lactate levels (0-24 hours before intervention)
- Maximum cardiac troponin levels (0-24 hours before intervention)
- Maximum NT-proBNP levels (0-24 hours before intervention)

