## 5.3 Diagnostic, Pre-, Peri- and Post-Intervention Variables

Following diagnostic variables will be collected and described:

- Time between diagnostic radiology and treatment (hours)
- Type of radiology (CT, angiography)
- Clinical presentation of PE (e.g. hypotension, syncope, cardiac arrest) (yes, no)
- Distribution of PE (unilateral, bilateral, saddle)
- Cardiac arrest before treatment (yes, no)
- ROSC before treatment (yes, no)
- Cardiac arrest during treatment (yes, no)
- Cardiac arrest after treatment (yes, no)
- ECMO initiated before treatment (yes, no)
- ECMO initiated during treatment (yes, no)
- ECMO initiated after treatment (yes, no)
- Extracorporeal cardiopulmonary resuscitation (ECPR) (yes, no)

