## 5.6 Confounders and Predictors

The confounders and predictors for the outcomes will be used in propensity scores and adjustments. All variables listed below will be included when building propensity scores. For the adjusted analyses, only the

strongest confounders and predictors will be part of the analyses. The number of confounders/predictors in the adjusted analyses will be based on the number of events available in the studied cohort. The general recommendation is to not have more than 1 variable/10 events in a statistical model. We will calculate the maximum number of variables in our study as N events/10.

The following variables will be investigated whether they are statistically defined confounders, i.e. related to both the intervention and the outcome:

- Contraindication for thrombolysis (8 categories)
- Insufficient previous effect of thrombolysis
- Cardiac arrest before treatment

The following variables will be investigated for their relation to the study outcomes:

- Age
- Sex
- Active cancer
- Invasive ventilation before treatment
- Circulatory instability
- Chronic heart failure
- Chronic pulmonary disease (COPD, asthma, other)
- Respiratory rate >30 beats/min
- Center

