Time to all-cause mortality will be investigated by using Cox proportional hazard model, describing HR with 95% CI and associated p-value following adjustment. Event rates, the number of events divided by total number of follow-up time will be described, together with the 95% CI obtained using exact 95% Poisson confidence limits. Graphically, this variable will be described applying Kaplan-Meier technique.

The confirmatory analyses will be performed for the following outcome variables, applying Bonferroni-Holm adjustment to minimize the Type I error:

- The primary composite outcome variable, death at 30 days and/or severe bleeding (according to GUSTO bleeding criteria) within 7 days after treatment
- The secondary outcome variable all-cause death at 30 days post-intervention
- The secondary outcome variable severe bleeding (according to GUSTO bleeding criteria) within 7 days after intervention
- The secondary outcome variable difference in RV/LV-ratio as compared before and after treatment

Additionally, the sensitivity analyses will be conducted applying adjustment for propensity score (PS) and PS 1:1 matching for the confirmatory analyses listed above, using the patients' background data to estimate the PS, performed by using logistic regression. Matching will be made applying nearest neighbour matching with the optimal caliper width of 0.2 of the standard deviation of the logit of the PS, as recommended. The performance will be validated by comparing the patient characteristics between the matched groups, that are expected not to differ, and described by standardized mean difference. The potential selection bias in the PS 1:1 matching will be examined in a drop-out analysis comparing included vs excluded FlowTriever® cases.

All non-confirmatory analyses will be evaluated in an exploratory manner at significance level of 0.05. All analyses will be performed using SAS software version 9.4 or later (SAS Institute Inc., Cary, NC, USA).

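### The propensity score list in SAP 5.6 omits ECMO before treatment and the measured pre-treatment blood pressure, heart rate and lactate, so primary and sensitivity analyses may share residual confounding by severity

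*SAP*

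**What the plan says.** SAP 5.6 gives an explicit rule for the PS: "All variables listed below will be included when building propensity scores". Its two lists hold twelve items: contraindication for thrombolysis, insufficient effect of earlier thrombolysis, cardiac arrest before treatment, age, sex, active cancer, invasive ventilation, circulatory instability, chronic heart failure, chronic pulmonary disease, respiratory rate above 30, and center. The limit of one variable per ten events is stated in the same section, for the adjusted analyses only.

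Sections 5.1 and 5.3 collect several pre-treatment severity measures that are not on that list:
- "ECMO initiated before treatment (yes, no" (5.3)
- "Minimum systolic blood pressure (0-24 hours before intervention" (5.1)
- "Maximum lactate levels (0-24 hours before intervention" (5.1)
- maximum heart rate over the same 24 hours (5.1)

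Troponin and NT-proBNP are also collected and not listed.

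Section 6.2 describes the PS more loosely, "using the patients' background data to estimate the PS", and does not refer to 5.6. Section 6.5 names two sensitivity analyses of the primary variable: adjustment for the PS, and 1:1 PS matching if at least 70% of FlowTriever patients find a match. Section 6.7 makes ECMO, including ECMO before the intervention, a subgroup variable.

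**The concern.** This is a retrospective, non-randomised comparison, and 30-day death is part of the primary endpoint. How ill a patient was before treatment can affect both the choice of treatment and the outcome. The primary model takes only the strongest items of the 5.6 list, and the PS takes the whole list. A severity marker absent from the list is therefore absent from all three analyses of the primary outcome. If such a marker is imbalanced and not well captured by the listed items, all three estimates move the same way, and their agreement says nothing about that bias.

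ECMO before treatment is the clearest gap, because the plan considers ECMO important enough to test for interaction but does not balance it.

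**Working it through.** **1. Severity items listed and collected**

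| Pre-treatment severity item | Collected in | In the 5.6 list |
|---|---|---|
| Cardiac arrest before treatment | 5.3 | yes |
| Ventilation | 5.1 | yes, as invasive ventilation |
| Respiratory rate | 5.1, as a maximum value | yes, cut at 30 |
| Circulatory instability | nowhere under that name | yes, undefined |
| ECMO before treatment | 5.3 | no |
| Minimum systolic pressure | 5.1 | no |
| Maximum heart rate | 5.1 | no |
| Maximum lactate | 5.1 | no |

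Four acute severity items are in the PS and four collected ones are not. The instability item could be built from pressure, heart rate, lactate, circulatory support or the hypotension entry under clinical presentation in 5.3. The SAP does not say which, nor how the item is coded.

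**2. Does the events rule explain the omission?** At the planning rates in 6.1, events are 60 × 0.20 + 200 × 0.40 = 92, which allows 9 variables in the outcome model. That cap does not apply to the PS, which takes every listed variable.

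**3. ECMO alone, no true treatment effect.** The SAP gives no prevalence or prognostic strength, so all inputs here are assumed. With baseline risk b and ECMO-outcome odds ratio R, the risk under ECMO is r = oR/(1 + oR), where o = b/(1 − b). The risk in a group with ECMO prevalence p is pr + (1 − p)b.

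Example with b = 0.35 and R = 5: o = 0.538 and r = 0.729. FlowTriever at p = 0.20: 0.20 × 0.729 + 0.80 × 0.35 = 0.426. Thrombolysis at p = 0.05: 0.05 × 0.729 + 0.95 × 0.35 = 0.369. Spurious odds ratio = (0.426/0.574)/(0.369/0.631) = 1.27.

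| ECMO prevalence, FlowTriever vs thrombolysis | R = 2 | R = 5 |
|---|---|---|
| 5% vs 5% | 1.00 | 1.00 |
| 10% vs 5% | 1.04 | 1.08 |
| 20% vs 5% | 1.11 | 1.27 |
| 30% vs 5% | 1.20 | 1.48 |

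The bias can also run the other way. With b = 0.30, R = 6 and prevalences of 5% (FlowTriever) vs 15%, r = 0.72, the group risks are 0.321 and 0.363, and the odds ratio is 0.83. Swapping the prevalences gives 1.21. These figures condition on no other covariate, so they overstate the bias to the extent that arrest and ventilation, which are in the PS, carry the same information.

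**4. A graded severity marker, partly covered by proxies.** Simulation with no treatment effect: 60 and 200 patients, 800 data sets, severity lower in FlowTriever patients. Thresholds and noise of the binary items are also assumed.

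| Imbalance; log-odds per SD | PS holds one noisy binary item | PS holds four |
|---|---|---|
| 0.5 SD; 0.5 | OR 0.83, 8% false positives | OR 0.89, 6% |
| 0.8 SD; 0.8 | OR 0.64, 26% | OR 0.73, 13% |

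Four items resemble the plan more closely than one. On the log scale they remove 1 − ln 0.89/ln 0.83 = 37% and 1 − ln 0.73/ln 0.64 = 29% of the single-item bias. The rest remains. In a companion run with one binary item, adding the continuous marker to the PS brought the odds ratio to 0.97–1.01 and false positives to 4–6%.

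**5. Size of the PS model.** Counting the eight contraindication categories as 7 terms, plus 10 single terms, gives 17 before center: 60/17 = 3.5 FlowTriever patients per term. Adding ECMO, systolic pressure and heart rate gives 60/20 = 3.0. Adding lactate as well gives 60/21 = 2.9.

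**The case against.** The strongest reply is that severity is already in the PS. The list names "Cardiac arrest before treatment", invasive ventilation, respiratory rate above 30 and "Circulatory instability", and the last may already carry pressure, heart rate or lactate. This stands as a limit on the size of the problem. It does not remove the problem, because the item is undefined and nothing says that it includes ECMO or graded values.

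Second, 6.2 checks matching by standardised mean differences, and Table 1.1 shows characteristics for the matched groups. Imbalance in lactate, pressure and heart rate should be visible there, since 5.1 calls them baseline characteristics. This also stands: the gap would not be wholly hidden. But seeing an imbalance does not correct it, and ECMO sits in 5.3, so its place in that table is not assured.

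Third, "background data to estimate the PS, performed by using logistic regression" in 6.2 may mean a wider set than 5.6. If so, the covariate set is not fixed. If it is only a general description, a cross-reference settles it.

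Fourth, extra terms strain a model with 60 FlowTriever patients, and section 6.4 pre-plans no imputation, so patients lacking a value could drop out of the PS. This stands as a reason for few additions and a missing-value rule.

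A reader might go further and infer that the omitted markers are the strongest ones, or that the PS analyses cannot remove confounding by severity. The document supports neither: it ranks no markers, and four acute severity items are in the score.

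**Conclusion.** The point holds as one of possible residual confounding. The omission is certain from the text. The consequence is conditional: nil if the omitted markers are balanced or well captured by the listed items, and material otherwise. On the assumed inputs, omitting ECMO alone gives spurious odds ratios between 0.83 and 1.48. An omitted graded marker gives 0.89 to 0.73 when four binary proxies are in the PS and FlowTriever patients are less ill. The SAP states neither the size nor the direction of any imbalance, so no direction of bias can be claimed. The stated power is unaffected. This is a cheap improvement to the specification.

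**What to change.** 1. In 5.6, add to the PS list ECMO before treatment and, as continuous values over the 24 hours before treatment, minimum systolic pressure and maximum heart rate. Add maximum lactate if it is sufficiently complete. If any of these is left out, give the reason.
2. Define circulatory instability from collected variables, or replace it with the continuous values. Replacement saves one term: 19 before center (3.2 FlowTriever patients per term), or 20 with lactate (3.0).
3. State a rule for missing PS covariates so that patients are not dropped. Section 6.4 gives its reason for outcomes only.
4. Make 6.2 refer to the 5.6 list in place of the general description.
5. Include ECMO before treatment in the planned standardised mean differences.

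The data are already being collected, so the cost is SAP wording plus the missing-value rule. The real downside is overlap. With more terms, the 70% condition in 6.5, which is 0.70 × 60 = 42 matched FlowTriever patients, may be harder to meet. If it is missed, the PS-adjusted analysis remains available.

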## 6 Statistical Methods

### 6.1 Sample Size

The few non-industry sponsored studies have been performed on a limited number of patients. Furthermore, there is an insufficiency of data concerning the outcomes in this particularly severe group of patients, making it challenging to make informed assumptions for a sample size calculation.

During the planned inclusion period, we anticipate enrolling 60 patients who will undergo the FlowTriever® procedure and 200 patients who will receive thrombolysis intervention. Assuming these group sizes and a 40% incidence rate of the composite outcome in the thrombolysis group, with a two-sided Fisher's exact test and an alpha level of 0.05, the FlowTriever® group would need to demonstrate a 50% reduction, equivalent to a 20% incidence of the composite outcome, to achieve a minimum of 80% statistical power. Our evaluation indicates that achieving such an outcome is feasible within the scope of this study, making it a viable candidate for a positive outcome.

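### Respiratory rate goes into the propensity score only as above or below 30, although the maximum value is collected; entering the value itself costs nothing, and the gain is modest and of unknown direction.

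*SAP*

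**What the plan says.** SAP section 5.1 lists among the baseline characteristics "Maximum respiratory frequency (0-24 hours before intervention", which is a numerical value. In section 5.6 the only form of this variable is "Respiratory rate >30 beats/min". No continuous version is listed and the cut is not explained. Age, in the same list, has no cut.

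Section 5.6 gives the listed variables two uses:

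- **Propensity score.** "All variables listed below will be included when building propensity scores". Respiratory rate is therefore certain to enter, in its binary form.
- **Adjusted models.** Only the "strongest confounders and predictors will be part of the analyses", under a cap: "We will calculate the maximum number of variables in our study as N events/10". Entry is conditional.

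Respiratory rate stands under the sentence "The following variables will be investigated for their relation to the study outcomes", not among the three variables to be examined as confounders. Under sections 6.2 and 6.5 the propensity score serves the sensitivity analyses (adjustment and 1:1 matching). The primary analysis is the adjusted logistic regression.

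**The concern.** The comparison is retrospective and non-randomised, and the propensity score is there to remove differences between the groups. An indicator at 30 treats rates of 12 and 29 as the same, and likewise 31 and 45. Two groups can therefore balance on the indicator and still differ in respiratory severity. If severity then affects death or bleeding in a graded way, part of that difference stays in the propensity-adjusted and matched odds ratios.

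There is a second, indirect route to the primary analysis. Section 5.6 admits only the strongest predictors to the adjusted model. If the relation to outcome is graded, the coarsened form looks weaker than the variable is, and is less likely to be selected.

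**Working it through.** **Inputs from the SAP.** Section 6.1 says "we anticipate enrolling 60 patients who will undergo the FlowTriever® procedure and 200 patients who will receive thrombolysis intervention", assumes "a 40% incidence rate of the composite outcome in the thrombolysis group", and takes 20% in the FlowTriever group. The SAP gives no figure for residual confounding. Its only computed figure is the power statement in 6.1. Exact enumeration of the two-sided Fisher test at 20% vs 40% gives 82.7%, so the stated minimum of 80% is met, but this has no bearing on the present point.

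**Inputs that must be assumed.** The share p of patients above 30, the shape of the distribution, the shape of the relation to outcome, and the imbalance between groups.

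**Step 1: what the indicator captures.** Let X be respiratory rate, standardised and normal, and D the indicator X > c, with p = P(X > c). Then Cov(X, D) = φ(c) and Var(D) = p(1 − p), so the squared correlation is φ(c)²/[p(1 − p)]. With linear effects, the share of X's confounding left after adjusting for D is approximately

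1 − φ(c)²/[p(1 − p)].

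For p = 0.50: φ(0)² = 0.159; 0.159/0.25 = 0.637; share left 0.363.

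| Share above 30 | Confounding left |
|---|---|
| 50% | 36% |
| 40% or 60% | 38% |
| 30% or 70% | 42% |
| 25% | 46% |
| 20% or 80% | 51% |
| 15% | 57% |
| 10% or 90% | 66% |
| 5% | 78% |

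**Step 2: check by simulation.** 400,000 patients per scenario, treatment odds 60:200 at the mean of X, no true treatment effect (OR 1.00), treatment log-odds slope 0.3 or 0.5 per SD, outcome OR 1.5 or 2 per SD. Share left = log OR adjusted for the indicator, divided by crude log OR.

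- 20-50% above 30: share left 36-52%; 10% above: 60-62%.
- Example (20% above, slope 0.5, outcome OR 2): crude OR 1.36, with the indicator 1.15, with the continuous value 1.00. ln 1.153 / ln 1.356 = 0.142/0.305 = 0.47.
- With the continuous value, OR 0.99-1.02 in all linear scenarios.

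**Step 3: departures from those assumptions.**

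- Risk truly steps at 30: the indicator gives OR 0.99-1.01, so about nothing is left. The linear term gave 1.005-1.017 there, in a simulation where treatment choice still depended linearly on X.
- A second adjuster correlated 0.4-0.6 with respiratory rate (slope 0.5, outcome OR 2, 20-50% above): share left 31-43%.
- Groups do not differ on respiratory rate: crude and indicator-adjusted OR both 0.99, so there is nothing to remove.

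**Step 4: size against precision.** With 40% events in both groups, the counts are 24 and 36 of 60, and 80 and 120 of 200. SE(log OR) = √(1/24 + 1/36 + 1/80 + 1/120) = 0.30. In the linear scenarios with 20-50% above 30, the OR left with the indicator is 1.06-1.15, a log OR of about 0.05-0.14, or roughly 0.2-0.5 SE.

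**Step 5: parameter cost.** At the plan's own rates, events = 60 × 0.20 + 200 × 0.40 = 12 + 80 = 92, so the cap is 92/10, about 9 variables. The indicator and a linear term each use one parameter. A 3-knot restricted cubic spline uses two.

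**The case against.** A fair defence of the plan has five parts.

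- **The primary model may never contain this variable.** This stands. Respiratory rate is not among the candidate confounders and must compete for a place. A reader might infer that the primary odds ratio is certain to carry this bias; the SAP does not support that. If the variable is not selected, its coding matters to the primary model only through the selection step.
- **The residual share is assumed, not known.** This also stands. A reader might take a third to a half of the confounding as a fact about this trial. The SAP supplies none of the inputs, and the range runs from about 0 to 78%. The near-perfect result for the continuous term partly reflects that the simulation generated a linear effect and then fitted one. The propensity score also holds invasive ventilation, circulatory instability and cardiac arrest, which may carry part of the same information.
- **Balance will be checked.** Section 6.2 compares patient characteristics in the matched groups by standardized mean difference, and Table 1.1 covers those groups. An imbalance in the maximum rate could therefore be seen, but the SAP states no remedy for it, and the check does not cover the propensity-adjusted analysis.
- **A linear term may be wrong, notably in ventilated patients.** Possibly. That argues for a more flexible term rather than for a cut, which imposes a flat risk on each side of 30. A spline is a real cost with about 60 treated patients and a score that already carries an eight-category contraindication variable and center, so it should be optional.
- **There is no contradiction.** Correct. Section 5.1 lists what is collected and described, and 5.6 defines model covariates. The point concerns an unexplained analysis choice.

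**Conclusion.** The point holds as a free improvement. The SAP discards information that it collects on a severity covariate, without a reason, in a propensity score whose purpose is to balance severity. Its certain reach is the propensity-adjusted and matched sensitivity analyses of the confirmatory outcomes. Its reach into the primary model depends on selection.

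Under a normal covariate with a linear effect, the share left is about 36-51% of the confounding carried by respiratory rate alone if 20-80% exceed 30, and more if few do. It is less if correlated adjusters are present, and about zero if risk steps at 30 or the groups are alike on it. In odds-ratio terms the effect is modest, at most about half a standard error in the 20-50% scenarios. Its direction is unknown, because the SAP does not say which group has the higher rates. None of this shows that the trial's conclusion would change.

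**What to change.** In section 5.6, replace the respiratory-rate line by: *maximum respiratory rate 0-24 hours before treatment (breaths/min), continuous*. State that it enters the propensity score as a linear term, and the adjusted model as a linear term if selected, with selection judged on the continuous form. A 3-knot spline in the propensity score is optional. Keep the >30 indicator for description only. The new line also corrects the unit.

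Cost: one line of SAP wording, no new data, and no extra parameter for the linear term, so the cap of one variable per ten events is unaffected. The optional spline adds one parameter, in the propensity score only.

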## 6 Statistical Methods

### 6.1 Sample Size

The few non-industry sponsored studies have been performed on a limited number of patients. Furthermore, there is an insufficiency of data concerning the outcomes in this particularly severe group of patients, making it challenging to make informed assumptions for a sample size calculation.

During the planned inclusion period, we anticipate enrolling 60 patients who will undergo the FlowTriever® procedure and 200 patients who will receive thrombolysis intervention. Assuming these group sizes and a 40% incidence rate of the composite outcome in the thrombolysis group, with a two-sided Fisher's exact test and an alpha level of 0.05, the FlowTriever® group would need to demonstrate a 50% reduction, equivalent to a 20% incidence of the composite outcome, to achieve a minimum of 80% statistical power. Our evaluation indicates that achieving such an outcome is feasible within the scope of this study, making it a viable candidate for a positive outcome.

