## 2 Study Objective and Hypothesis

The objective of this study is to evaluate catheter-directed intervention with the FlowTriever® device by comparison to contemporary systemic thrombolysis in patients with acute PE.

The hypothesis is that patients treated with the FlowTriever® device will have lower incidence of the primary outcome variable, the composite endpoint death at 30 days and/or severe bleeding (according to GUSTO bleeding criteria) within 7 days after treatment, than patients treated with contemporary thrombolysis.

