### 6.2 General Methodology

Descriptive statistics will be used for group characteristics and outcomes. Mean, standard deviation, median, and range will be described for the continuous variables and frequency and percentage for categorical variables. Intergroup comparisons considering baseline characteristics will be done using Fisher's exact test for

dichotomous variables, Chi-square test for non-ordered categorical variables, and the Mann-Whitney U-test for continuous variables.

The comparative analyses between the groups considering the dichotomous study outcomes will be performed using logistic regression adjusted for known and statistically identified confounders (variables that are related both to the study group and the outcome). Odds-ratios (OR) with associated 95% CI, p-values and area under the receiver operating characteristic curve (AUC-ROC) will be presented. Hosmer-Lemeshow test will be performed as a goodness-of-fit test.

The comparative analyses between the groups considering the continuous study outcomes will be performed using linear regression adjusted for known and statistically identified confounders. Model assumptions will be checked by reviewing diagnostic plots, and if needed transformation (e.g. log) of the outcome variable will be performed. Least square means with associated 95% CI, p-values and  $R^2$  will be presented.

Outcome variables length of stay in ICU (hours) and length of hospital admission (days) will be handled as continuous variables in the case of no censored patients. In case of censored patients in the database, time to discharge will be studied using Cox proportional hazard model, resulting in hazard ratios (HR) with 95% CI and p-value. Proportional hazards assumptions will be checked graphically. Otherwise, the variables will be studied as continuous variables using either linear regression assuming normal distribution if applicable or Poisson or negative binomial regression depending on the distribution of the variables. Results from the Poisson and negative binomial regression result in risk ratio (RR) with 95% CI and p-value.

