## 6.3 Adjustment for Type I Error

As per above in the General Methodology Bonferroni-Holm adjustment will be used for the confirmatory analyses. All other tests will be exploratory.

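### The power of at least 80% in SAP 6.1 is for a single test at 0.05, but SAP 6.2 and 6.3 test the composite in a four-outcome Bonferroni-Holm family, where the same test has between 64.0% and 82.7% power

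*SAP*

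**What the plan says.** SAP section 2 states one hypothesis, on the composite of death at 30 days and/or GUSTO severe bleeding within 7 days: "The hypothesis is that patients treated with the FlowTriever® device will have lower incidence of the primary outcome variable".

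SAP 6.1 anticipates 60 FlowTriever and 200 thrombolysis patients and assumes 40% incidence under thrombolysis. It applies a two-sided Fisher's exact test "and an alpha level of 0.05, the FlowTriever® group would need to demonstrate a 50% reduction", that is 20% incidence, "to achieve a minimum of 80% statistical power". It concludes that such a result is feasible, "making it a viable candidate for a positive outcome".

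SAP 6.2 sets the testing rule: "The confirmatory analyses will be performed for the following outcome variables, applying Bonferroni-Holm adjustment to minimize the Type I error". Four outcomes follow: the composite, 30-day death, severe bleeding, and the change in RV/LV-ratio. SAP 6.3 repeats that "Bonferroni-Holm adjustment will be used for the confirmatory analyses". An unadjusted 0.05 is mentioned only for the rest: "All non-confirmatory analyses will be evaluated in an exploratory manner at significance level of 0.05".

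The planned comparison for binary outcomes, including the primary (SAP 6.2 and 6.5), is "logistic regression adjusted for known and statistically identified confounders (variables that are related both to the study group and the outcome"), not Fisher's test.

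**The concern.** The power is computed at one significance level and the outcome is tested under a different rule. Bonferroni-Holm orders hypotheses by p-value, so being listed first, or being called primary, gives the composite no priority. SAP 6.1 makes no allowance for this.

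What is at stake is how the main result is read. The composite carries the study's only stated hypothesis, and 6.1 rests its optimism about a positive result on this figure. A non-significant primary result would be taken to come from a test with at least 80% power to detect a halving, which the planned rule does not guarantee. Conversely, some results that count as success under 6.1 would not be significant under 6.2 and 6.3 unless other outcomes were rejected too.

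**Working it through.** **Inputs.** From SAP 6.1: n = 60 (FlowTriever) and 200 (thrombolysis), incidences 0.20 and 0.40, two-sided Fisher's exact test, alpha 0.05. From SAP 6.2 and 6.3: four hypotheses under Bonferroni-Holm.

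**Formula.** Exact power at level a is the sum, over all tables (x, y) whose two-sided Fisher p-value is ≤ a, of Bin(x; 60, 0.20) × Bin(y; 200, 0.40).

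**Step 1: the plan's own figure.** At a = 0.05 the sum is 0.8273. The claim of at least 80% reproduces for a single test.

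**Step 2: the Holm levels.** With four hypotheses the successive levels are 0.05/4, 0.05/3, 0.05/2 and 0.05. The third column is the FlowTriever incidence at which power reaches 80%, with control kept at 40%.

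| Level | Power at 20% vs 40% | Incidence for 80% power | Relative reduction |
|---|---|---|---|
| 0.0125 | 64.0% | 17.3% | 56.9% |
| 0.0167 | 67.9% | 17.8% | 55.4% |
| 0.025 | 74.1% | 18.8% | 52.9% |
| 0.05 | 82.7% | 20.6% | 48.5% |

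**Step 3: what Holm requires of the composite.**

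- p ≤ 0.0125: rejected whatever the other outcomes show.
- 0.0125 < p ≤ 0.0167: at least one other outcome must be rejected.
- 0.0167 < p ≤ 0.025: at least two must be rejected.
- 0.025 < p ≤ 0.05: all three must be rejected.

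Power under Holm for this test is therefore at least 64.0% and at most 82.7%. The share of studies with 0.0125 < p ≤ 0.05 is 0.8273 − 0.6395 = 0.1878, or 18.8%.

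**Step 4: what it would take to reach 80%.** In the most favourable case every study with p ≤ 0.025 is rejected, which gives 0.7405. Let q be the proportion of studies with 0.025 < p ≤ 0.05 in which all three other outcomes are rejected. Then 0.7405 + q × (0.8273 − 0.7405) ≥ 0.80 requires q ≥ 0.0595/0.0868 = 0.685. The SAP gives no effects for death, severe bleeding or RV/LV from which q could be judged.

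**Step 5: concrete results.** With 80/200 events under thrombolysis:

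- 13/60 gives p = 0.0093: significant regardless.
- 14/60 gives p = 0.021: needs two other rejections.
- 15/60 gives p = 0.046: needs all three.
- 16/60 gives p = 0.068: not significant under either rule.

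**Step 6: the planned model.** None of these figures bounds the power of the adjusted logistic regression. As an illustration on assumptions that are not in the SAP, take one binary covariate present in 50% of FlowTriever and 10% of thrombolysis patients, with marginal incidences held at 20% and 40%. For covariate-outcome odds ratios of 0.5, 1 and 2, simulated Wald power (4,000 runs each) is 26%, 54% and 81% at 0.0125, and 49%, 76% and 94% at 0.05. Because the marginal incidences are fixed, the conditional treatment odds ratio also changes across the three cases (about 0.48, 0.375 and 0.27), and this contributes to the spread. Only the middle case isolates the cost of imbalance: 54% against 63% with a balanced covariate, at 0.0125. The example shows only that adjusted power can fall on either side of the Fisher figure.

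**The case against.** The strongest reply is that nothing in 6.1 is miscalculated. It names its test, sidedness, alpha, group sizes and control rate, and under those conditions 82.7% meets the stated minimum. That is right: the fault is a mismatch between sections, not a slip in arithmetic.

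Second, 64.0% is a floor, and Holm is less strict than Bonferroni. Also right, and the range is the proper statement. But it does not rescue 80%. Death and severe bleeding are components of the composite, so neither can have more events than it does. In simulations under several assumed splits of the composite into death and bleeding, with RV/LV ranging from no effect to certain rejection, power for the composite under Holm was about 64% to 75%. Those splits are assumptions, not a bound for every case.

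Third, the consequence is limited. The study is retrospective over a fixed window, the group sizes are anticipated counts, 6.1 itself admits that informed assumptions are hard to make, and the odds ratio with its 95% CI will be reported whatever the p-value. All of this stands and limits the severity, but it does not make the power statement correct.

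Fourth, sizing on a simple test when an adjusted model is planned is common practice. That is so; the difference between Fisher and logistic regression is a secondary point that needs a sentence in 6.1, not a new calculation.

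**Conclusion.** The concern holds. The minimum of 80% power is correct for one unadjusted Fisher test at 0.05, but it is not supported under the plan's own testing rule. For that same test, at 60 versus 200 patients and 20% versus 40%, power under Bonferroni-Holm lies between 64.0% and 82.7%, and only the lower figure is assured without assumptions about the other three outcomes. At the first Holm level, 80% power needs a reduction of about 57%, not 50%.

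The figures rest on the incidences and group sizes in 6.1 and on the Fisher test; power of the planned adjusted regression may differ in either direction. Type I error, estimates, confidence intervals and the number of patients are not affected. The fault is in the power statement, and it should be fixed before analysis.

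**What to change.** Restate SAP 6.1 before analysis to say three things:

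1. The 80% claim (exact value 82.7%) is for one unadjusted two-sided Fisher test at 0.05, before any multiplicity adjustment.
2. At the first Holm level of 0.0125 the same test has 64.0% power at 20% versus 40%, and reaches 80% at a FlowTriever incidence of about 17%. Any power quoted under Holm must state the effects assumed for death, severe bleeding and RV/LV.
3. The primary analysis is an adjusted logistic regression, whose power may be higher or lower than the Fisher figure.

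This is wording only; no data, sample or analysis changes.

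If the sponsor instead intends the composite to be tested at the full 0.05, SAP 6.2 and 6.3 must say so: test the composite first, and apply Bonferroni-Holm to the three secondary outcomes only if it is significant. The cost is that no confirmatory secondary claim is possible when the primary fails. Point 1 (without its multiplicity clause) and point 3 would still be needed. The choice is the sponsor's, and it should be made before results are known so that the p-values cannot influence it.
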